13.5 Reporting and Exclusions

13.5.1 **Evaluation of toxicity** – All patients will be evaluable for toxicity from the time of their first treatment with ARQ 197 (tivantinib)/ Cetuximab. (also see 11.1.1).

13.5.2 **Evaluation of response** – All patients included in the study must be assessed for response to treatment, even if there are major protocol treatment deviations or if they are ineligible unless they are not evaluable as defined under 11.1.1.

Each patient will be assigned one of the following categories: 1) complete response, 2) partial response, 3) stable disease, 4) progressive disease, 5) early death from malignant disease, 6) early death from toxicity, 7) early death because of other cause, or 9) unknown (not assessable, insufficient data). [Note: By arbitrary convention, category 9 usually designates the “unknown” status of any type of data in a clinical database.]

All of the patients who met the eligibility criteria (with the possible exception of those who received no study medication (see 11.1.1)) should be included in the main analysis of the response rate. Patients in response categories 4-9 should be considered to have a treatment failure (disease progression). Thus, an incorrect treatment schedule or drug administration does not result in exclusion from the analysis of the response rate. Precise definitions for categories 4-9 will be protocol specific.

All conclusions should be based on all eligible, response evaluable patients (see 11.1.1). Subanalyses may then be performed on the basis of a subset of patients, excluding those for whom major protocol deviations have been identified (*e.g.*, early death due to other reasons, early discontinuation of treatment, major protocol violations, etc.). However, these subanalyses may not serve as the basis for drawing conclusions concerning treatment efficacy, and the reasons for excluding patients from the analysis should be clearly reported. The 95% confidence intervals should also be provided.

APPENDIX A

Performance Status Criteria

ECOG Performance Status Scale		Karnofsky Performance Scale	
Grade	Descriptions	Percent	Description
0	Normal activity. Fully active, able to carry on all pre-disease performance without restriction.	100	Normal, no complaints, no evidence of disease.
		90	Able to carry on normal activity; minor signs or symptoms of disease.
1	Symptoms, but ambulatory. Restricted in physically strenuous activity, but ambulatory and able to carry out work of a light or sedentary nature (e.g. , light housework, office work).	80	Normal activity with effort; some signs or symptoms of disease.
		70	Cares for self, unable to carry on normal activity or to do active work.
2	In bed <50% of the time. Ambulatory and capable of all self-care, but unable to carry out any work activities. Up and about more than 50% of waking hours.	60	Requires occasional assistance, but is able to care for most of his/her needs.
		50	Requires considerable assistance and frequent medical care.
3	In bed >50% of the time. Capable of only limited self-care, confined to bed or chair more than 50% of waking hours.	40	Disabled, requires special care and assistance.
		30	Severely disabled, hospitalization indicated. Death not imminent.
4	100% bedridden. Completely disabled. Cannot carry on any self-care. Totally confined to bed or chair.	20	Very sick, hospitalization indicated. Death not imminent.
		10	Moribund, fatal processes progressing rapidly.
5	Dead.	0	Dead.

APPENDIX B

CTEP MULTICENTER GUIDELINES

If an institution wishes to collaborate with other participating institutions in performing a CTEP sponsored research protocol, then the following guidelines must be followed.

Responsibility of the Protocol Chair

- The Protocol Chair will be the single liaison with the CTEP Protocol and Information Office (PIO). The Protocol Chair is responsible for the coordination, development, submission, and approval of the protocol as well as its subsequent amendments. The protocol must not be rewritten or modified by anyone other than the Protocol Chair. There will be only one version of the protocol, and each participating institution will use that document. The Protocol Chair is responsible for assuring that all participating institutions are using the correct version of the protocol.
- The Protocol Chair is responsible for the overall conduct of the study at all participating institutions and for monitoring its progress. All reporting requirements to CTEP are the responsibility of the Protocol Chair.
- The Protocol Chair is responsible for the timely review of Adverse Events (AE) to assure safety of the patients.
- The Protocol Chair will be responsible for the review of and timely submission of data for study analysis.

Responsibilities of the Coordinating Center

- Each participating institution will have an appropriate assurance on file with the Office for Human Research Protection (OHRP), NIH. The Coordinating Center is responsible for assuring that each participating institution has an OHRP assurance and must maintain copies of IRB approvals from each participating site.
- Prior to the activation of the protocol at each participating institution, an OHRP form 310 (documentation of IRB approval) must be submitted to the CTEP PIO.
- The Coordinating Center is responsible for central patient registration. The Coordinating Center is responsible for assuring that IRB approval has been obtained at each participating site prior to the first patient registration from that site.
- The Coordinating Center is responsible for the preparation of all submitted data for review by the Protocol Chair.
- The Coordinating Center will maintain documentation of AE reports. There are two options for AE reporting: (1) participating institutions may report directly to CTEP with a copy to the Coordinating Center, or (2) participating institutions report to the Coordinating Center who in turn report to CTEP. The Coordinating Center will submit AE reports to the Protocol Chair for timely review. Audits may be accomplished in one of two ways: (1) source documents and research records for selected patients are brought from participating sites to the Coordinating Center for audit, or (2) selected patient records may be audited on-site at participating sites. If the NCI chooses to have an audit at the Coordinating Center, then the Coordinating Center is responsible for having all source documents, research records, all IRB approval documents, NCI Drug

Accountability Record forms, patient registration lists, response assessments scans, x-rays, etc. available for the audit.

Inclusion of Multicenter Guidelines in the Protocol

- The protocol must include the following minimum information:
 - The title page must include the name and address of each participating institution and the name, telephone number and e-mail address of the responsible investigator at each participating institution.
 - The Coordinating Center must be designated on the title page.
 - Central registration of patients is required. The procedures for registration must be stated in the protocol.
 - Data collection forms should be of a common format. Sample forms should be submitted with the protocol. The frequency and timing of data submission forms to the Coordinating Center should be stated.
 - Describe how AEs will be reported from the participating institutions, either directly to CTEP or through the Coordinating Center.
 - Describe how Safety Reports and Action Letters from CTEP will be distributed to participating institutions.

Agent Ordering

Except in very unusual circumstances, each participating institution will order DCTD-supplied investigational agents directly from CTEP. Investigational agents may be ordered by a participating site only after the initial IRB approval for the site has been forwarded by the Coordinating Center to the CTEP PIO.

APPENDIX C

Tissue Sample Collection Form
NCI 9165: ARQ 197 (tivantinib)/Cetuximab -- HNC

Clinician/Research Nurse: Please Fill Out	
Tissue Samples	
Patient Name: _____	MRN# (if applicable): _____
Patient Protocol ID #: _____	Date Tissue Obtained: _____
Institution: _____	Attending Physician: _____
Site of Biopsy: _____	Site of Primary Tumor: _____
Did Surgical Pathology review tissue for presence of tumor (please circle)? Yes No	
Number of unstained slides (10-14 slides (5 µm thick),)	
Number of 5 µm slides: _____	
Blood collection (please check):	
Two EDTA tubes (purple top, serum), 2x10ml: ____ (e.g. BD#366643 EDTA (K2)) or similar	One SST tube 7.5ml (gold top): _____ (e.g BD#: 367987 SST, 7.5ml) or similar_ (If volume is <7.5ml provide additional tube/s)__
Date of blood draw: _____	Time of blood draw: _____
Contact Person's Phone Number and email Address at Affiliate:	

Shipment Address:

University of Chicago
[name]
[name]
[name]
[contact]
E-mail: [contact]

Please notify [name] with the tracking number once the sample was shipped:

Email: [contact]
[contact]

Disclaimer: Cost of packaging and shipment cost, as well as procurement of shipping materials and courier service shipping supplies are the responsibility of each center and appropriate internal budgeting is mandatory for participation in this trial. A reference sheet outlining summarizing appropriate shipping procedures will be provided to each center.

APPENDIX E

Management of Cetuximab induced acneiform rash

Patients developing dermatologic toxicities while receiving cetuximab should be monitored for the development of inflammatory or infectious complications.

Treatment of acneiform rash should be initiated early starting with grade 2. Dose modifications of any future cetuximab infusions are listed in the protocol and should be considered for severe (grade 3/4) acneiform rash.

Rash can be managed by a variety of treatment options to relieve symptoms and improve rash. The recommendations for management are as follows:

—> Grade 1 rash: Mild, Grade 1 rash may not need treatment, but close monitoring is to be initiated to .

—> Grade ≥ 2 rash: May be treated with any of the following:

- Minocycline/doxycycline
- Diphenhydramine
- topical retinoid
- topical clindamycin
- topical silver sulfadiazine

APPENDIX F

PATIENT'S MEDICATION DIARY

Agent: ARQ 197 (Tivantinib)

CTEP-assigned Protocol # _____
Local Protocol # _____

Today's date _____

Patient Name _____ (initials acceptable)

Patient Study ID _____

1. Complete one form for each cycle of treatment.
2. **ARQ 197 (Tivantinib)** should be stored at room temperature.
3. **ARQ 197 (Tivantinib)** tablets should be administered orally with meals. A missed or vomited dose should not be replaced, thus should take the next scheduled dose at the regularly scheduled time.
4. Record the date, the time, and the number of **ARQ 197 (Tivantinib)** capsules taken per day (2 administrations/day).
5. If you have any comments or notice any side effects, please record them in the Comments column.
6. Please bring this form and your bottles of **ARQ 197 (Tivantinib)** when you return for each appointment.

Day	Date	Time of First Dose	Dose taken	Time of Second Dose	Dose taken	Comments
			# of capsule taken		# of capsule taken	
1						
2						
3						
4						
5						
6						
7						
8						
9						
10						
11						
12						
13						
14						
15						
16						
17						
18						
19						
20						
21						
22						
23						
24						
25						
26						
27						
28						

Patient's Signature: _____

Cycle: _____

Date: _____

Physician's Office will complete this section:

1. Date patient started protocol treatment _____
2. Date patient was removed from study _____
3. Patient's planned total daily dose _____
4. Total number of capsules taken this Month _____
5. Cycle Number _____
6. Physician/Nurse/Data Manager's Signature _____

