5. TREATMENT PLAN

Patients are randomized between two arms (see schema below):

1. cetuximab 500mg/m² iv, every two weeks, PLUS ARQ 197 (tivantinib) 360mg BID, by mouth
2. cetuximab 500mg/m² iv, every two weeks

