5.1.1 ARQ 197 (tivantinib) administration

- Patients receive ARQ 197 (tivantinib) on an outpatient basis. The starting dose is 360 mg, by mouth, twice daily.
- The patient will be requested to maintain a medication diary of each dose of medication. The medication diary will be returned to clinic staff at the end of each cycle. A sample medication diary can be requested from the University of Chicago or can be provided by the respective treatment center using a local template.
- ARQ 197 (tivantinib) tablets should be administered orally with meals. A missed or vomited dose (= not taken within 4 hours (i.e. 4 hours before or after) the scheduled time) should not be replaced. The patient should be instructed to take the next scheduled dose at the regularly scheduled time.

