9.1.1.5 Site(s) Performing Correlative Study: The University of Chicago

10. STUDY CALENDAR

Schedules shown in the Study Calendar below are provided as an example and should be modified as appropriate.

Baseline evaluations are to be conducted within 16 days prior to start of protocol therapy. Scans and x-rays must be done ≤ 4 weeks prior to the start of therapy. In the event that the patient's condition is deteriorating, laboratory evaluations should be repeated within 48 hours prior to initiation of the next cycle of therapy.

	Pre-Study	Wk 1	Wk 2	Wk 3	Wk 4	Wk 5	Wk 6	Wk 7	Wk 8	Wk 9	Wk 10	Wk 11 and every 2 weeks thereafter	Wk 12	Off Study ^c
ARQ 197 (tivantinib)		A------(given twice daily)-----A												
Cetuximab		B		B		B		B		B		B		
Informed consent	X													
Demographics	X													
Medical history	X													
Concurrent meds	X	X-----X												
Physical exam	X	X		X		X				X		every 4 wks		X
Vital signs	X	X		X		X				X		x		X
Height	X													
Weight	X	X		X		X		X		X		x		X
Performance status	X	X		X		X				X				X
CBC w/diff, plts	X	X	X	X	X	X	X	X	X	X	X	X	X	X
Research Blood draw	X													
Serum chemistry ^a	X	X	X	X	X	X	X	X	X	X	X	X	X	X
EKG (at baseline then as indicated)	X	X												
Adverse event evaluation		X-----X												X
Tumor measurements	X	Tumor measurements are repeated every 8 weeks. Documentation (radiologic) must be provided for patients removed from study for progressive disease.												X
Radiologic evaluation	X	Radiologic measurements should be performed every 8 weeks.												X
B-HCG	X ^b													
Unstained slides of tumor	X													

A: *ARQ 197 (tivantinib)*: Dose as assigned; *po twice daily*
B: *Cetuximab*: Dose as assigned; *every two weeks*
a: Albumin, alkaline phosphatase, total bilirubin, bicarbonate, BUN, calcium, chloride, creatinine, glucose, LDH, phosphorus, potassium, total protein, SGOT [AST], SGPT [ALT], sodium, magnesium
b: Serum pregnancy test (women of childbearing potential).
c: Off-study evaluation.
Starting week 5 – MD visits are only required every 4 weeks, unless more frequent visits are medically indicated.

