12.1 Data Reporting

12.1.1 Method

This study will be monitored by the Clinical Data Update System (CDUS) version 3.0. Cumulative CDUS data will be submitted quarterly to CTEP by electronic means. Reports are due January 31, April 30, July 31, and October 31. Instructions for submitting data using the CDUS can be found on the CTEP web site (<http://ctep.cancer.gov>). **Note:** All adverse events that have occurred on the study, including those reported through CTEP-AERS, must be reported via CDUS.

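### Only the tivantinib diary asks patients to write down side effects, so low-grade symptoms may be captured more completely in the combination arm

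*Combined protocol and SAP*

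**What the plan says.** Section 5 randomizes patients to cetuximab plus tivantinib or to cetuximab alone. The cetuximab schedule, "cetuximab 500mg/m² iv, every two weeks", is common to both arms; tivantinib is the only oral study drug.

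The diary appears in the body of the protocol only under tivantinib administration (Section 5.1.1), where it is described as a dose record: "The patient will be requested to maintain a medication diary of each dose of medication". It then goes to the site: "The medication diary will be returned to clinic staff at the end of each cycle". The same section says that the form "can be provided by the respective treatment center using a local template", as an alternative to the sample from the coordinating center.

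The sample form in Appendix F names tivantinib as its agent and has a Comments cell for each of 28 days. Item 5 reads: "If you have any comments or notice any side effects, please record them in the Comments column". Item 6 asks the patient to bring the form to each appointment.

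Clinic ascertainment is set out once for everyone. The Section 10 calendar has a row "Adverse event evaluation" running through treatment and at the off-study visit, with no distinction by arm. Section 12.1.1 adds: "All adverse events that have occurred on the study, including those reported through CTEP-AERS, must be reported via CDUS". Section 13.6 says that the randomization is not blinded.

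**The concern.** In an open-label randomized comparison of toxicity, adverse events should be sought in the same way in each arm. Here one arm has a standing written prompt with a space for every day, and the other has none. From week 5 the calendar requires physician visits only every four weeks, so a written note can preserve a mild symptom that would otherwise be forgotten by the next visit.

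The symptoms most exposed are those that both drugs are said to cause. Section 7.1 lists fatigue, nausea and diarrhea as possibly related to tivantinib. Section 2.3 gives rates of 48% asthenia/malaise, 29% nausea and 25% diarrhea for cetuximab monotherapy. For such symptoms only the comparison between randomized arms can show what tivantinib adds. If mild cases are found more often in one arm because of the form, part of an apparent excess would come from how the data were collected. Unlike sampling error, this would most plausibly push in one direction.

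**Working it through.** **1. Who is prompted.** Combination arm: Section 5.1.1 and Appendix F apply from the start of treatment. Cetuximab-alone arm: no diary, symptom sheet or equivalent appears in the documents. A control patient who takes tivantinib after progression would come under Section 5.1.1 only then. So the asymmetry exists during randomized treatment.

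**2. Whether a diary note becomes an adverse event record.** Staff receive the form, and Sections 7.5 and 12.1.1 require all adverse events to be reported, so the route is open. It is not specified, however. The office-completed part of Appendix F covers dates, planned dose, number taken, cycle and signature; it has no line for reviewing comments. Section 7.3 requires a CTCAE term, a grade and an attribution, none of which a patient's comment supplies. Practice could differ by site.

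**3. What the plan gives on size.** It gives no capture rates and no expected low-grade event rates for this comparison. Its only sample-size figure is for response (Section 13.2): 12% versus 35%, one-sided alpha 0.10, 80% power, continuity-corrected. I checked that figure because it supplies the arm size used below.

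- Uncorrected: n0 = [1.2816 × √(2 × 0.235 × 0.765) + 0.8416 × √(0.12 × 0.88 + 0.35 × 0.65)]² / 0.23² = 29.7.
- Corrected: n = (n0/4) × [1 + √(1 + 4/(n0 × 0.23))]² = 37.9, so 38 per arm, as stated.

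This calculation does not depend on the diary. The 38 counts response-evaluable patients; the toxicity population (all treated) may be slightly larger.

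**4. Illustration under assumptions.** Let the true rate p be the same in both arms, with capture c_T = 0.90 with the diary and c_C between 0.60 and 0.90 without it. Then

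- false excess = p × (c_T − c_C);
- standard error = √{[a(1 − a) + b(1 − b)]/38}, where a = p × c_C and b = p × c_T.

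| True rate p | Excess at c_C = 0.90 | Excess at c_C = 0.60 | SE at c_C = 0.60 | Excess / SE |
|---|---|---|---|---|
| 20% | 0 | 18 − 12 = 6 points | 8.2 points | 0.7 |
| 30% | 0 | 27 − 18 = 9 points | 9.5 points | 0.9 |
| 50% | 0 | 45 − 30 = 15 points | 11.0 points | 1.4 |

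Applying the same 0 to 30 point gap to the Section 2.3 rates:

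- asthenia/malaise: 0.48 × 0.30 = 14.4 points at most (5.5 of 38 patients);
- nausea: 0.29 × 0.30 = 8.7 points at most (3.3 of 38);
- diarrhea: 0.25 × 0.30 = 7.5 points at most (2.9 of 38).

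The lower end is zero in each case. The Section 2.3 figures are already reported rates from other cetuximab trials, so they indicate scale and are not true rates for this population.

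**The case against.** A reader might infer that the excess toxicity attributed to tivantinib is inflated as a matter of fact. The documents do not support that, for four reasons.

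- No section names the diary as a source of adverse event data, and Section 5.1.1 describes it as a dose record that patients are asked, not obliged, to keep.
- Item 5 is one conditional line beside a general comments column, not a symptom checklist, and a site's own template may omit it.
- Both arms follow the same adverse event row and laboratory schedule, and both attend every two weeks for cetuximab. A patient is missed in an incidence table only if the symptom goes unrecorded at every contact, so the diary's extra yield could be nil.
- Toxicity is not a primary or secondary objective, and Section 13 plans no between-arm toxicity test. The one numerical rule concerns severe toxicities in the first 6 combination patients.

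All four stand. They reduce the claim from bias shown to bias possible, and limit it to descriptive comparison of grade 1-2 symptoms. They do not remove the asymmetry. The prompt exists in one arm only, the route into the data is left open, and Section 13.5.1 makes all treated patients evaluable for toxicity, so rates by arm can be set side by side and read. The local-template option may dilute any effect, but it also adds variation between sites.

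**Conclusion.** The point holds as a possible, one-directional bias in descriptive comparison of low-grade, subjective adverse events (fatigue, nausea, diarrhea). Its size cannot be determined from the documents and may be zero. With equal true rates of 20% to 50% and an assumed capture gap of 0 to 30 points, the false excess is 0 to 15 percentage points, at most about 1.4 standard errors with 38 per arm. That range depends wholly on the assumed gap.

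Response rate, tumor shrinkage, PFS and OS do not use the diary. Laboratory events follow one blood-test schedule in both arms. Severe events, including those counted in the early toxicity rule, are likely to come to notice without a diary. These are unaffected or little affected. Priority is low.

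**What to change.** Move the side-effect prompt out of the tivantinib dosing diary and onto a one-page, 28-day symptom sheet given in identical form to all randomized patients. Add a sentence to Section 7 stating that adverse events are elicited by the same questions at the same visits in both arms.

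If the diary is kept as it is, add a case report form flag for adverse events whose only source is the diary, and present the by-arm table of grade 1-2 events with and without them.

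The cost is one extra patient sheet or one case report form flag, with a small added burden for patients and data entry. Sample size, visits and treatment do not change.
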